3.3 Exclusion Criteria

Subjects meeting any of the following criteria must not be enrolled in the study:

1. Subjects who have current active hepatic or biliary disease (with the exception of patients with Gilbert's syndrome, asymptomatic gallstones, liver metastases or stable chronic liver disease per investigator assessment).
2. Having received rituximab within the prior 2 months
3. Treatment with any known therapeutic or experimental therapy within 4 weeks prior to enrollment, or currently participating in any other interventional clinical study
4. Other past or current malignancy. Subjects who have been free of malignancy for at least 5 years, have a history of completely resected non-melanoma skin cancer, successfully treated in situ carcinoma, adequately treated basal or squamous cell skin cancer, adequately treated Stage I or II cancer from which the patient is currently in complete remission, or any other cancer for which the patient has been disease-free for 5 years are eligible.
5. Prior treatment with anti-CD20 monoclonal antibody or alemtuzumab within 2 months prior to start of therapy.
6. Chronic or current infectious disease requiring systemic antibiotics, antifungal, or antiviral treatment such as, but not limited to, chronic renal infection, chronic chest infection with bronchiectasis, tuberculosis and active Hepatitis C.
7. History of significant cerebrovascular disease in the past 6 months or ongoing event with active symptoms or sequelae
8. Known HIV positive
9. Clinically significant cardiac disease including unstable angina, acute myocardial infarction within six months prior to randomization, congestive heart failure (NYHA III-IV), and arrhythmia unless controlled by therapy, with the exception of extra systoles or minor conduction abnormalities.
10. Significant concurrent, uncontrolled medical condition including, but not limited to, renal, hepatic, gastrointestinal, endocrine, pulmonary, neurological, cerebral or psychiatric disease which in the opinion of the investigator may represent a risk for the patient.
11. Positive serology for Hepatitis B (HB) defined as a positive test for HBsAg. In addition, if negative for HBsAg but HBcAb positive (regardless of HBsAb status), a HB DNA test will be performed and if positive the subject will be excluded. HBsAg negative, HBsAB negative, HBsAB positive subjects can be included, * See Monitoring criteria for HBcAb+ and HBV DNA negative subjects on next page.
 - Consult with a physician experienced in care & management of subjects with hepatitis B to manage/treat subjects who are anti-HBc positive

12. Positive serology for hepatitis C (HC) defined as a positive test for HCAb, in which case reflexively perform a HC RIBA immunoblot assay on the same sample to confirm the result
13. Pregnant or lactating women. Women of childbearing potential must have a negative pregnancy test at screening. **women of child bearing potential must undergo pregnancy testing prior to each dose if the previous pregnancy test was greater than 14 days prior and a pregnancy test at 6 months after the last dose.
14. Women of childbearing potential, including women whose last menstrual period was less than one year prior to screening, unable or unwilling to use adequate contraception from study start to one year after the last dose of protocol therapy. Adequate contraception is defined as hormonal birth control, intrauterine device, double barrier method or total abstinence.
15. Male subjects unable or unwilling to use adequate contraception methods from study start to one year after the last dose of protocol therapy.
16. Receiving warfarin

*Monitoring criteria for HBcAb+ and HBV DNA negative subjects:

- If HBV DNA is negative, subject may be included but must undergo at least every 2 month HBV DNA PCR testing from the start of treatment during the treatment course.
- Monitoring during the follow-up period will be performed during routine study visits for a minimum follow-up period of six months after the last dose, as long as the subject remains on study. Monitoring frequency during follow-up should occur at a minimum of every 2-3 months. Whenever possible, the monitoring should occur as part of the routine follow-up visit (Note: for most studies, the follow-up visits are 1 month post-dose, 3 months post-dose and 6 months post-dose).
- Prophylactic antiviral therapy may be initiated at the discretion of the investigator.

3.4 Withdrawal Criteria

[figure not shown]
Subjects may be withdrawn from the study at any time if it is the wish of the subject (or their legally acceptable representative) for any reason, the investigator judges it necessary due to medical reasons including disease progression or the subject becomes pregnant. (See also Section 7.4.7) The subject will be evaluated for disease status and survival per the follow-up visit schedule outlined in Section 7.1.

The reason for withdrawal from study participation must be documented.

4.0 INVESTIGATIONAL PLAN

Study Design

TREATMENT SCHEMA

This is an open-label, Phase II study of ofatumumab in patients with relapsed or refractory CLL. Twelve doses of ofatumumab as currently approved over a 24 week period with 2 units of FFP with each dose (with exception of the first dose) will be administered. Ofatumumab will be infused intravenously on day 1 (300 mg initial dose), followed one week later by 2000 mg weekly for 7 doses, followed 4 weeks later by 2000 mg every 4 weeks for 4 doses. Two units (approximately 200 or 250 ml) of FFP will be administered prior to ofatumumab.

The study period will consist of screening, treatment, and follow-up (see Section 7.1 for study calendar and assessments schedule).

5.0 STUDY TREATMENT

5.1 Ofatumumab

Novartis will supply ofatumumab vials presented as 100 mg – acetate formulation, 20 mg/mL, 5 mL fill vials, and 1000 mg – acetate formulation, 20 mg/mL, 50 mL fill vials.

The study medical product, ofatumumab, is a liquid concentrate for solution for infusion presented in glass vials. Ofatumumab will be infused intravenously on day 1 (300 mg initial dose), followed one week later by 2000 mg weekly for 7 doses, followed 4 weeks later by 2000 mg every 4 weeks for 4 doses.

The ofatumumab infusions will be prepared in 1000 mL NaCl sterile, pyrogen free 0.9% NaCl to yield a 0.3 mg/mL, or 2 mg/mL ofatumumab concentration for infusions of 300 mg or 2000 mg, respectively.

Ofatumumab vials must be stored at 2-8°C. Protect from light and do not freeze. No special packaging components, other than the outer white cardboard carton in which the vials are placed, will be used to afford light protection.

Ofatumumab open-labeled product will be for intravenous infusion. Our site is responsible for labeling individual vials for study use.

All items required for administration of study medication (e.g., infusion bags, filters, etc.) will be provided by University of California Davis Comprehensive Cancer Center.

5.1.1 Ofatumumab Pre-Medication

Pre-medication before each ofatumumab infusion must be given within 30 minutes to 2 hours prior to the treatment (Table 5-1).

Table 5-1 Pre-medication Requirements Prior to Ofatumumab Infusions

Infusion #	Acetaminophen (po) or equivalent	Antihistamine (iv or po) diphenhydramine or equivalent	Glucocorticoid (iv) prednisolone or equivalent
1 st	1000 mg	50 mg	50 mg
2 nd	1000 mg	50 mg	50 mg
3 rd -N th	1000 mg	50 mg	0 – 50 mg*

*If the 2nd infusion has been completed without the subject experiencing any grade = 3 AEs, pre-medication with glucocorticoid may be reduced or omitted before the 3rd to Nth infusion at the discretion of the investigator.

5.1.2 Composition of Ofatumumab Injection 20 mg/mL

The quantitative composition of acetate formulation is 20 mg/mL. This is available in two fill volumes, 5 mL / vial (100 mg/vial) and 50 mL/vial (1000 mg/vial).

Ingredient	Quantity/ mL
Ofatumumab	20.0 mg
Sodium Acetate, Trihydrate	6.80 mg
Edetate Disodium, Dihydrate (EDTA)	0.019 mg
Polysorbate 80	0.20 mg
L-Arginine	10.0 mg
Sodium Chloride	2.98 mg
Hydrochloric Acid	to give pH 5.5
Water for Injection	q.s. to 1.0 mL

5.1.3 Preparation of Ofatumumab Infusion

Ofatumumab will be prepared as 1000 mL dilution of ofatumumab in sterile, pyrogen-free 0.9% NaCl. The exact time of dilution into the 0.9% NaCl must be written on the label of the infusion bag.

Once diluted into saline, the product is stable for up to 24 hours at ambient temperature. However, the product contains no preservative and should be used as soon as possible after dilution.

Preparation of drug solution for intravenous injection by the site pharmacist or designee will be done in accordance with the protocol, and in these dilution instructions. Ofatumumab intravenous solution will

be prepared using standard dilution methods and following general aseptic practice standard to preparation of IV medications. Eyes and hands should be protected when handling ofatumumab.

For intravenous administration, compatibility of the following components for ofatumumab in clinical studies (i.e., not for commercial product) has been established:

Table 5-2 Dosing Components for Ofatumumab in Clinical Studies

Dosing component	Material of construction	Suggested Vendor
1L Saline Bags	Polyvinyl Chloride (PVC)	Baxter
	Polyolefin [polyethylene* (PE)/polypropylene (PP)]	Baxter, B. Braun
Administration Set	PVC	Baxter
	PVC lined with Polyethylene	B. Braun
Filter Extension Set	Sterilizing-grade (0.22 μ m) hydrophilic filter	Durapore brand by Millipore
	Lines made of PVC, filter membrane material polyether sulfone	Baxter
	Lines made of PVC lined with Polyethylene, filter membrane material polyether sulfone	Alaris/Cardinal Health

Preparation of the 1000 mL infusion bags should be done on the day of planned infusion.

* polyethylene (IUPAC name: polyethene)

5.1.3.1 Materials for Preparation and Administration of Infusion

The following materials are needed when preparing and administering the infusion:

1000 mL sterile pyrogen free 0.9% saline (NaCl) infusion bag(s). The solution can be kept at ambient temperature for a maximum of 24 hours after preparation; however, the product does not contain a preservative and dosing should begin as soon as possible after dose preparation.

Ofatumumab 100 mg and 1000 mg vials (supplied by Novartis)

Needles and syringes (50 mL sterile syringe) not supplied by Novartis

Intravenous (IV) cannula (not required if subject has central venous access) [not supplied by Novartis]

Infusion pump and infusion tubing set (not supplied by Novartis)

In-line low protein binding, polyether sulfone filter 0.2 μ m (please make sure a spare filter is available in case the filter needs to be changed) [not supplied by Novartis]. Please note that the commercial filters are sterilizing-grade (0.22 μ m) hydrophilic Durapore by Millipore.

5.1.3.2 Dilution of Ofatumumab

- Ensure the correct container number is used.
- Take a 1000 mL infusion bag (sterile pyrogen free 0.9% saline), remove and dispose of the appropriate amount of saline according to Table 5-3 or Table 5-4
- Draw the required amount of ofatumumab according to Table 5-3 (100 mg vials) or Table 5-4 (1000 mg vials) below
- Inject ofatumumab into the saline bag
- Invert the infusion bag slowly 3 times, avoiding formation of any foam
- Label the infusion bag with the completed label

Table 5-3 Preparation of Ofatumumab Infusion: 100 mg vials

Dose of Ofatumumab	Infusion bag size	Volume of NaCl to be removed from infusion bag	Volume of ofatumumab (number of ofatumumab vials)
300 mg	1000 mL	15 mL	15 mL (3 vials, 5 mL/vial)
2000 mg	1000 mL	100 mL	100 mL (20 vials, 5 mL/vial)

Table 5-4 Preparation of Ofatumumab Infusion: 1000 mg vials

Dose of Ofatumumab	Infusion bag size	Volume of NaCl to be removed from infusion bag	Volume of ofatumumab (number of ofatumumab vials)
2000 mg	1000 mL	100 mL	100 mL (2 vials, 50 mL/vial)

5.1.4 Ofatumumab Infusion Set up

Ofatumumab must be administered by i.v. infusion through an in-line filter and through a well-functioning i.v. catheter (i.v. cannula) into a vein in the arm (or other venous access) by an infusion pump.

Please Note: It is mandatory to use an in-line low protein binding 0.2 micron polyether sulfone filter for all IV dosing of ofatumumab drug product.

DO NOT ADMINISTER AS AN INTRAVENOUS PUSH OR BOLUS.

Ofatumumab should not be mixed with any other medication. If ofatumumab is to be dosed through an in-dwelling catheter, then, any previous medication should be removed by flushing with normal saline prior to dosing with ofatumumab.

- Check subject ID against the label on the infusion bag and ensure the expiry of the solution. The solution must be administered in its entirety to the subject within 24 hours from time of preparation.
- Attach the 1000mL infusion bag to the infusion set (if not done at the pharmacy).
- Attach the in-line filter to the infusion set (closest to the subject; see Figure 1). **Note: The in-line filter must be used during the entire infusion.**
- Prime the infusion set and filter with ofatumumab (if not done at the pharmacy).
- In case of a problem with the filter (i.e. clogging/blockage), please change, re-prime the new filter, and continue the infusion.
- In case of problem with infusion set, follow local procedures.
- Check the backflow from the i.v. cannula according to routine practice at site
- Set the pump at the initial infusion rate 12mL/hr for the first infusion and 25mL/hr for the subsequent infusions (if no grade ≥ 3 infusion-associated AEs were observed in the previous infusion)
- Start the infusion using the following infusion rates

Table 5-5 Infusion rate of 1st ofatumumab infusion (300 mg)

[figure not shown]
Time	mL/hour
0 – 30 minutes	12
31 – 60 minutes	25
61 – 90 minutes	50
91 – 120 minutes	100
121 - 150 minutes	200
151 - 180 minutes	300
181+ minutes	400

Table 5-6 Infusion rate of subsequent ofatumumab infusion

Time	mL/hour
0 – 30 minutes	25
31 – 60 minutes	50
61 – 90 minutes	100
91 – 120 minutes	200
121+ minutes	400

No ofatumumab dose modifications are permitted.

Figure 1 Infusion Set-Up Schematic

6.0 FRESH FROZEN PLASMA ADMINISTRATION

Fresh frozen plasma will be administered per University of California Davis Health System GUIDELINES FOR ADULT TRANSFUSION (Patient Care Standards, XIII-12) (Approved by Medical Staff Executive Committee 11/06).

7.0 STUDY ASSESSMENTS AND PROCEDURES

7.1 Study Calendar and Assessment Schedule

All visits should be +/- 7 business days with the exception of day 1 of cycle 1.

Procedures	≤ 14 days prior to registration[†]	Treatment				Follow-up	
		Doses 1-4 (Every week – Week 1, 2, 3, 4)	Doses 5-8 (Every week – Week 5, 6, 7, 8)	Doses 9-12 (Every 4 weeks - Week 12, 16, 20, 24)	Treatment withdrawal	1,3, 6 months following last ofatumumab dose	9, 12, 15, 18, 21, 24 months following last ofatumumab dose
Medical History	X						
Disease History	X						
Therapy History	X						
Efficacy Assessments							
¹ Bone marrow/ aspirate biopsy	X					X	
² CT/PET	X					X	X
Safety Assessments							
³ Physical Exam or Evaluation	X	³ X	³ X	³ X		X	X
³ ECOG	X	³ X	³ X	³ X		X	X
Height	X						
Weight	X					X	X
Vital Signs	X	X	X	X		X	
12-lead ECG	X						
Adverse Events		X	X	X	X	X	X
⁴ FFP (2 units)		⁴ X	X	X			
Dispense Study Medication							
Ofatumumab		X	X	X			
Lab Assessments							
⁵ Hematology	X	X	X	X		X	X
⁶ Chemistry	X	X	X	X		X	X
⁷ Liver chemistry	X	X	X	X			
⁸ Complement levels	X	X		X		X	X

Procedures	< 14 days prior to registration[†]	Treatment				Follow-up	
		Doses 1-4 (Every week – Week 1, 2, 3, 4)	Doses 5-8 (Every week – Week 5, 6, 7, 8)	Doses 9-12 (Every 4 weeks - Week 12, 16, 20, 24)	Treatment withdrawal	1,3, 6 months following last ofatumumab dose	9, 12, 15, 18, 21, 24 months following last ofatumumab dose
⁹ B-cells, IgG, IgA and IgM	X					X	
¹⁰ HIV Test	X						
¹¹ Serum Pregnancy Test	X						
Hepatitis B&C*	X						X
Survival	X					X	X

***REQUIRED- Subjects who are HBcAb positive** must undergo at least every 2 month HBV DNA PCR testing during the treatment course. Monitoring must also occur during the follow-up period for a minimum of 6 months after the last dose as long as the subject remains in the study at a minimum frequency of every 2 to 3 months.

[†] Bone marrow/aspirate biopsy and CT/PET performed within 28 days of registration.

1. BM biopsy will be performed for staging at baseline and if clinically warranted after completion of therapy. If the BM biopsy is positive at baseline it must be repeated once to confirm CR. This will include flow cytometry for minimal residual disease (MRD) status. Bone marrow (or peripheral blood if bone marrow is unavailable must be sent to the cytogenetics laboratory for analysis. If the BM biopsy is negative at baseline, it will not be repeated.
2. CT/PET will be performed for staging at baseline and if clinically warranted after completion of therapy.
3. Patient will see treating physician for physical exam/evaluation and ECOG evaluation every 4 weeks.
4. Two units of FFP will be given with each dose of ofatumumab with the exception of the first dose of ofatumumab.
5. During the treatment phase, obtain hematology pre-treatment and every 2 weeks for the first month, then every month thereafter for at least 6 months after the last dose of ofatumumab.
6. Chemistries include electrolytes, BUN, creatinine and lactate dehydrogenase (LDH). During the treatment phase, obtain chemistries pre-treatment and every 2 weeks for the first month, then every month thereafter for at least 6 months after the last dose of ofatumumab or up to discretion of investigator.
7. Liver chemistries consist of albumin, INR, ALT, AST, total bilirubin, and alkaline phosphatase. During the treatment phase, obtain liver chemistries pre-treatment and every 2 weeks for the first month, then every month thereafter for at least 6 months after the last dose of ofatumumab.
8. Complement will be measured at baseline, before and after the first and second dose of ofatumumab, at week 12, 16, 20 and 24, at completion of therapy, and at follow up only in patients with low complement levels at baseline or after treatment.
9. B-cells, IgG, IgA and IgM will be monitored until they return to baseline or up to two years after the last dose of ofatumumab, or until the subject starts other B-cell depleting therapy.
10. Human Immunodeficiency Virus (HIV) test; If status is unknown.
11. Women of childbearing potential must have a negative pregnancy test at screening. **women of child bearing potential must undergo pregnancy testing prior to each dose if the previous pregnancy test was greater than 14 days prior and a pregnancy test at 6 months after the last dose.

7.2 Efficacy

Efficacy analyses will be performed on data from the Intent-to-Treat Population.

Definition of Response

Response criteria	NCI-WG National Cancer Institute – Working Group	IWCLL International Workshop on Chronic Lymphocytic Leukemia
Complete Response (CR):		
Physical exam (nodes, and/or liver, spleen)	Normal	Normal
Symptoms	None	None
Lymphocytes ($\times 10^9/L$)	≤ 4	<4
Neutrophils ($\times 10^9/L$)	≥ 1.5	
Platelets ($\times 10^9/L$)	> 100	
Hb (g/dL)	>11 (untransfused)	Not stated
Bone marrow lymphocytes (%)	>30 ; no nodules	Normal, allowing nodules or focal infiltrates
Partial Response (PR):		
Physical exam (nodes, and/or liver, spleen)	$\geq 50\%$ decrease	Downshift in stage
Plus ≥ 1 of:		
Neutrophils ($\times 10^9/L$)	≥ 1.5	
Platelets ($\times 10^9/L$)	>100	
Hemoglobin (g/dL)	>11 or 50% improvement	
Duration of CR or PR	≥ 2 months	Not stated
Progressive disease (PD):		Upshift in stage
Physical exam (nodes, liver, spleen)	$\geq 50\%$ increase or new	
Circulating lymphocytes	$>50\%$ increase	
Other	Richter's syndrome	
Stable disease (SD):	All others	No change in stage

Bone Marrow Examination

A bone marrow aspirate and biopsy are generally not required to make the diagnosis of CLL. Nevertheless, CLL is a disease of the bone marrow, and it is appropriate to evaluate a major site of involvement. The aspirate smear must show $\geq 30\%$ of all nucleated cells to be lymphoid. A bone marrow examination also provides useful prognostic information by determining whether there is diffuse or non-diffuse involvement, and permits an assessment of the erythroid precursors and megakaryocyte.

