2.0 BACKGROUND AND RATIONALE

2.1 Chronic Lymphocytic Leukemia (CLL)

Chronic Lymphocytic Leukemia is the most common type of leukemia in the Western world, accounting for 40% of all leukemia types in people over the age of 65 [Oscier, 2004]. It is estimated that in the US alone 15,110 adults (8,750 men and 6,360 women) were diagnosed and 4,390 adults will die of CLL in 2008 [Jemal, 2008]. The prevalence of CLL increases with age and the median age at the time of diagnosis is 65 to 70 years [Redaelli, 2004]. Approximately 50% of patients are initially asymptomatic and are observed for several years before treatment is needed, therefore more than half of patients who finally require therapy are older than 70 years. The disease is a hematological neoplasm of unknown etiology, characterized by accumulation of monomorphic small, round mature-appearing B lymphocytes in the peripheral blood, bone marrow, and lymph nodes that aberrantly co-express T-cell (CD5+) and B-cell (CD19+, CD23+) cell surface markers, with a low expression of CD20. Over the past decade, new information suggests B-CLL originates from antigen-stimulated mature B-lymphocytes, which either avoid cell death through the effect of external signals, or die by apoptosis, but are replenished by proliferating precursor cells [Chiorazz, 2005]. CLL follows a variable clinical course with overall survival times ranging from months to decades. Median survival from diagnosis is approximately 10 years in the overall CLL population, but is only 18 months for patients with advanced disease [Nabhan, 2004]; and 9-13 months for CLL cases refractory to fludarabine [Byrd, 2004].

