2.3 Ofatumumab

Ofatumumab is a fully human monoclonal antibody (mAb), IgG1κ, targeting a unique epitope on the CD20 molecule expressed on human B-cells, resulting in increased binding affinity to CD20, prolonged dissociation rate, and increased cell kill due to greater complement dependent cytotoxicity (CDC) activity and similar antibody dependent cell mediated cytotoxicity (ADCC) activity, especially in low CD20 expressing cells [Teeling, 2006]. Thus, depletion of B-cells by ofatumumab treatment may provide clinical benefits to subjects with CD20-expressing cell tumors. In B-CLL, the goal of treatment is to achieve complete abnormal B-cell depletion in the blood and to induce an objective tumor response in the lymph nodes.

In a Phase I dose-ranging trial of ofatumumab 500mg (n=3), 1000mg (n=3), or 2000mg (n=27) given weekly x 4, 50% PR was observed in the 2000mg dose amongst relapsed CLL patients [Coiffier, 2008]. Objective response significantly correlated with maximum observed concentration (Cmax), minimum observed concentration (Cmin), area under the concentration-time curve (AUC), and half-life ($t^{1/2}$) and survival endpoints correlated with exposure. The maximum tolerated dose (MTD) was not reached and

treatment was well tolerated. Adverse events were limited to grade 1-2 infusion reactions and easily managed with premedication. Grade 3-4 neutropenia occurred in only 6% of patients. Non-opportunistic grade 1-2 infections were observed in 51% of patients.

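### The NCI-WG partial-response rule has no blood-lymphocyte criterion, although CR and PD in the same column do, and nothing says whether PR or PD prevails when both are met

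*Combined protocol and SAP*

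**What the plan says.** Section 7.2 tabulates response under two headings, NCI-WG and IWCLL, and does not say which governs. The NCI-WG column reads as follows (counts in 10⁹/L, haemoglobin in g/dL).

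- **CR** requires a normal exam, no symptoms, lymphocytes ≤4, neutrophils ≥1.5, platelets >100, untransfused haemoglobin >11, and a marrow criterion.
- **PR** requires a ≥50% decrease on the row beginning "Physical exam (nodes, and/or liver, spleen", plus at least one of neutrophils ≥1.5, platelets >100 or haemoglobin ">11 or 50% improvement". The row "Duration of CR or PR" adds at least 2 months. There is no lymphocyte row.
- **PD** lists a ≥50% increase or new disease on exam, a >50% increase in "Circulating lymphocytes", and Richter's syndrome. The reference point for the lymphocyte increase (baseline or nadir) is not given.
- The row beginning "Stable disease (SD" takes every remaining patient.

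In the IWCLL column PR is "Downshift in stage", also without a lymphocyte row. No sentence ranks PR against PD.

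Section 2.1 describes the disease as an accumulation of "mature-appearing B lymphocytes in the peripheral blood, bone marrow, and lymph nodes". Section 2.3 says that "the goal of treatment is to achieve complete abnormal B-cell depletion in the blood", and names a nodal tumour response beside it. Section 3.2 requires a pathological diagnosis but no palpable disease. Section 8.2 bases the go/no-go decision on CR + PR. Sections 1.0 and 8.1 also place PFS in the primary endpoint.

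**The concern.** The PR rule measures disease burden by physical exam only. Its count condition uses absolute thresholds, so a patient who enters with one adequate count has already met it. For that patient, PR rests on the exam and its duration alone. Blood disease, which the plan treats as a disease site and a treatment target, affects CR and PD but not PR.

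PR is likely to be where the endpoint is decided. The pivotal-trial interim results in section 2.3 list 30 + 34 = 64 partial responses and 1 complete response, so 64 of 65 responders were PRs. A PR rule that misclassifies some patients therefore acts directly on the count compared with the section 8.2 boundaries. The missing ranking of PR and PD also reaches the other part of the primary endpoint, because the PD rows in section 7.2 are the only definition of progression in the document.

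**Working it through.** **1. The plan's own design figure.** Inputs from section 8.2: null rate 25%, target 45%, one-sided 5%, power at least 80%, stop at ≤4 of 17, active at ≥14 of 36. The probability of declaring activity at true rate p is

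P(p) = Σ (x = 5 to 17) Bin(x; 17, p) × Pr[Bin(19, p) ≥ 14 − x].

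This gives P(0.25) = 0.0437 and P(0.45) = 0.8002. The stated design reproduces, so the problem is in what is counted as a response.

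**2. NCI-WG rows side by side.**

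| | Exam | Lymphocytes | Other counts | Duration |
|---|---|---|---|---|
| CR | normal | ≤4 | all three | ≥2 months |
| PR | ≥50% decrease | none | any one | ≥2 months |
| PD | ≥50% increase or new | >50% increase | none | none |

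**3. The rows applied to example patients.** The PD rows are read as alternatives. Requiring all of them, Richter's syndrome included, would not be workable.

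- (a) No palpable nodes or organs, lymphocytes from 150 to 2, platelets 150, haemoglobin 10.5. Section 3.2 admits this patient (haemoglobin ≥9.0). CR fails because 10.5 is not above 11. PR fails because a site that was never enlarged cannot shrink by 50%. The result is stable disease, although lymphocytes fell by (150 − 2)/150 = 98.7%.
- (b) Nodes down 50%, lymphocytes up 45%, one adequate count. The PR rows are met. The PD row is not, since 45% is below 50%.
- (c) As (b), but lymphocytes up 60%. The PR rows and the PD lymphocyte row are both met.

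**4. Size per patient.** 1/12 = 8.3 percentage points and 1/36 = 2.8 points, against 45% − 25% = 20 points. Both sample sizes are shown because sections 3.1 and 8.2 differ. That conflict is a separate matter.

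**5. Sensitivity on assumed rates.** The documents give no misclassification rate, so the fractions below are assumptions, run through the step 1 formula.

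| Share of true responders not scored | Effective rate | Power |
|---|---|---|
| 0% | 45.0% | 0.80 |
| 5% | 45% × 0.95 = 42.8% | 0.72 |
| 10% | 45% × 0.90 = 40.5% | 0.62 |
| 20% | 45% × 0.80 = 36.0% | 0.40 |

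In the other direction, if 2 or 5 percentage points of patients are wrongly scored PR when the true rate is 25%, the type I error rises from 0.044 to 0.077 or 0.155.

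**The case against.** Several limits stand. Because PR and CR must last at least 2 months, no PR is final at one visit. Patient (c) meets the criteria for both categories on the same day but does not yet have a confirmed PR. What is missing is a sentence saying whether the lymphocyte rise cancels the PR.

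A reader might infer that cleared blood disease can never count as PR. The table does not support that. A patient with nodal disease and cleared blood can be PR through the exam row, and a patient without palpable disease can still reach CR. The gap concerns blood clearance without a qualifying exam decrease, in a patient who misses a CR row.

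A reader might also infer that blood depletion is the leading treatment goal. Section 2.3 names blood depletion and nodal response without ranking them, and the exam row does measure the second.

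Nor do the documents show that cases (b) and (c) occur. They need nodes to halve while lymphocytes rise on an antibody for which section 7.4.1 treats B-cell depletion as an expected effect. Upward misclassification is a consequence of the rule, not an observed rate.

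Finally, the table condenses published guidelines, and a row could have been lost when the text was extracted. That is speculative: the PR block reads as complete and the lymphocyte rows under CR and PD survive. If the IWCLL column governs, the examples do not carry over as written, but its PR has no lymphocyte row either.

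**Conclusion.** The point holds for the NCI-WG column as written. It is a stated rule that gives wrong or contradictory classifications in identifiable patients. It rests on two readings: that the PD rows are alternatives and that the PR block is complete.

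The size can be stated only per patient: 8.3 points of response rate at 12 patients or 2.8 at 36. The documents give neither the distribution of disease sites nor a frequency of discordant responses. No share of the sample can therefore be said to be lost, and the power and type I error figures are illustrations only. Since CR + PR drives the decision and PFS is also primary, the rule should be corrected before responses are scored.

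**What to change.** Revise the NCI-WG rows in section 7.2 as follows.

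1. Add a PR lymphocyte row: a decrease of at least 50% from baseline when the baseline count is above the table's own CR limit of 4 × 10⁹/L.
2. Require the node or liver/spleen decrease only where that site is enlarged at baseline.
3. Require at least one of nodes, liver/spleen or blood to be abnormal at baseline, and every abnormal one to meet its threshold. Without this, a patient with marrow disease only would become PR by default on one adequate count.
4. State that PD takes precedence over PR, and that the PD lymphocyte row does not apply while the count stays within the CR limit. Otherwise a nodal responder going from 1.0 to 1.6, a 60% rise, would be called progressed.
5. Keep the count and 2-month conditions, and check the revised rows against the guidelines cited in section 10.

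Under these rules, with the duration met, patient (a) becomes PR. With a baseline count above 4, patient (b) becomes stable and patient (c) becomes PD.

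The cost is one table row and a few sentences. No assessment is added: section 7.1 already schedules hematology, and the CR and PD rows already need the lymphocyte count. The small downside is that a node-only responder with persistent lymphocytosis would no longer count as PR.
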